The esophageal microbiome is very similar to the oral microbiome; both contain an abundance of anaerobes as well as a high ratio of Firmicutes to Bacteroidetes. The microbiome of the upper gastrointestinal tract is presumably heavily influenced by migration of bacteria from the mouth via swallowed secretions. Therefore, it stands to reason that altering the oral microbiome can directly impact the microbiome of the esophagus and gastric cardia. Chlorhexidine has broad antimicrobial effects, and chlorhexidine-based mouthwashes have been used clinically for many years in the treatment of gingival and other oral diseases. Chlorhexidine mouthwash effectively reduces anaerobes and *F. nucleatum* in particular in the mouth. It also has anti-inflammatory effects (likely due to reductions in pro-inflammatory bacteria), and protects against mucositis in chemotherapy patients. We therefore propose to perform a randomized open-label pilot study to assess the effects of chlorhexidine mouthwash on the microbiome of the gastric cardia. The results of this study provide valuable information as to whether altering the oral microbiome can serve as a novel chemopreventive intervention to reduce the risk of esophageal adenocarcinoma.

This is a randomized, open-label pilot study to assess whether treatment with chlorhexidine mouthwash can alter the esophageal and gastric cardia microbiome.

We will enroll a total of 20 subjects. Patients scheduled for upper endoscopy for clinical indications will be randomized to 2 weeks of either no treatment or use of twice daily chlorhexidine mouthwash leading up to the endoscopy.

The hypotheses to be tested are:

1. Treatment with chlorhexidine mouthwash will significantly reduce the absolute abundance of *F. nucleatum* in saliva.
2. Subjects treated with chlorhexidine mouthwash will have significantly lower absolute abundance of *F. nucleatum* in the gastric cardia, compared to subjects who receive no treatment.

We will enroll patients scheduled for upper endoscopy by their treating physician and who meet the inclusion and exclusion criteria. There will be 2-3 study visits, at Day 0 and Day 14, and for

those subjects in the mouthwash arm, a final visit 1-2 weeks following the Day 14 visit. Subjects will be required to fast overnight prior to the visits on Days 0 and 14.

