**Statistics:**

The primary outcome will be the absolute abundance of *F. nucleatum*. To address the hypothesis that chlorhexidine mouthwash reduces the absolute abundance of *F. nucleatum* in the mouth, we will assess within individual differences in subjects treated with chlorhexidine and in those who received no treatment.

We will calculate mean and standard deviation for the within-individual change in *F. nucleatum* for the treated and untreated arms. These two means will then be compared using t-tests. For the primary analysis will use data from the saliva samples, and will then perform secondary analyses with data from the oral swab samples.

We will then address the hypothesis that subjects treated with chlorhexidine have lower abundance of *F. nucleatum* in the gastric cardia compared to those who did not receive treatment. We will calculate the mean absolute abundance of *F. nucleatum* in the cardia of the treated and untreated groups, and compare means using t-tests. We will then analyze data in a similar fashion from esophageal brushings in secondary analyses. All analyses will be 2- sided. For the primary analyses, statistical significance will be defined as  $p < 0.05$ .

We will perform numerous additional secondary analyses as part of this pilot study. For each subject and sample collected we will calculate the relative abundance of Gram-negative bacteria (%GNB). We will then make the same comparisons described above, with %GNB as the outcome. For these analyses we will use Wilcoxon rank sum tests instead of t-tests.

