Additional 16S sequencing analyses. For secondary analyses related to the microbiome, sequences will be grouped into operational taxonomic units (OTUs) of 97% similarity. Using these OTU definitions, we will estimate the microbial diversity of a sample by calculating distance measures based on various metrics, including the Shannon diversity index (alpha diversity), and Unifrac. This includes adjusting for the number of taxa detected for their relative abundance (proportions). We will align a representative set of OTU sequences and assign taxonomy based on the most recent Greengenes OTU database. We will phylogenetically assess phyla-level differences in relative abundance between groups, as well as exploratory analyses of the relative abundance of individual taxa, using the BenjaminiHochberg method to adjust for multiple hypothesis testing. We will normalize data with the R packages phyloseq and DESeq2. We will perform Principal Coordinate Analysis (PCA) and Hierarchical clustering of specimens based on phyla-level phylogeny or count-based distance metrics to compare groups of samples. Finally, we will perform PICRUSt analyses to estimate and compare the functional metagenomic compositions of the samples using the 16S data.

Other secondary analyses. We will compare the treated and untreated groups in terms of levels of the above prespecified inflammatory cytokines and markers of stem cell proliferation and intestinalization. We will also review the pre- and post- photographs of the mouth of the mouthwash arm subjects to determine the proportion of subjects who developed staining. The individual assessing the images will be blinded as to which images are pre- or post- treatment. We will use t-tests and Wilcoxon rank sum tests to compare continuous data and Fisher exact

tests for categorical data between groups. All analyses will be 2-sided, and statistical significance will again be defined as  $p < 0.05$ .

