**Sample Size Considerations:**

There is no published data on which to base power calculations for this study.

Prior studies have demonstrated that chlorhexidine mouthwash significantly reduces *F. nucleatum* in the mouth. However, these studies used older techniques to quantify *F. nucleatum*, and the results cannot be readily translated to expected findings using qPCR.

A sample size of 20 subjects (10 per arm) has 83% power (assuming  $\alpha = 0.05$ ) to detect a 1.3 SD difference in mean *F. nucleatum* between the groups, which likely represents a biologically meaningful difference. As this is a pilot study, we believe that in the event no significant reduction in *F. nucleatum* is observed, we will still obtain valuable data from the secondary analyses that will assist in the design of future studies aimed at altering the microbiome to reduce the risk of BE and EAC.

We anticipate that 10% of enrolled subjects will be excluded, removed, or lost to follow-up. We therefore plan to enroll 22 subjects.

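### Overall community composition is compared only by ordination and clustering, so the planned UniFrac distances carry no test or effect size by arm

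*Combined protocol and SAP*

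**What the plan says.** The design statement near the start of the protocol gives the purpose as to "assess whether treatment with chlorhexidine mouthwash can alter the esophageal and gastric cardia microbiome". The two hypotheses listed there are narrower: both concern F. nucleatum, one in saliva and one in the gastric cardia.

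The Statistics section follows the hypotheses: "The primary outcome will be the absolute abundance of" F. nucleatum, compared between arms by t-test. The Gram-negative share of each sample is a secondary outcome: "For these analyses we will use Wilcoxon rank sum tests instead of t-tests".

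In the same section, under Additional 16S sequencing analyses, the plan describes "calculating distance measures based on various metrics, including the Shannon diversity index (alpha diversity), and Unifrac". It provides for phylum-level comparisons and "exploratory analyses of the relative abundance of individual taxa, using the BenjaminiHochberg method to adjust for multiple hypothesis testing". For communities taken as a whole it names principal coordinate analysis and "Hierarchical clustering of specimens based on phyla-level phylogeny or count-based distance metrics to compare groups of samples". The section closes with a general rule for other comparisons: "We will use t-tests and Wilcoxon rank sum tests to compare continuous data and Fisher exact" tests for categorical data, two-sided at 0.05.

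No global test of between-sample distance is named anywhere, and no single distance is chosen.

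**The concern.** Ordination and clustering are unsupervised. They arrange samples by their largest differences, take no account of arm, and produce neither an error rate nor an estimate of how much variation arm explains. Yet the plan gives comparing groups as their purpose. With 10 points against 10, a partial separation on a plot cannot be told from chance by eye, and a modest real difference need not form its own cluster.

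What is at stake is one part of the stated question: whether overall composition at the cardia and in the esophagus differs by arm. Under Sample Size Considerations, the protocol relies on the secondary analyses to inform later studies if F. nucleatum shows no significant reduction. A later study would want a tested and sized community effect, and the plan as written does not produce one.

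**Working it through.** **1. The plan's only power figure.** "A sample size of 20 subjects (10 per arm) has 83% power" for a difference of 1.3 SD. By the normal approximation, 1.3/√(2/10) = 2.907, then 2.907 − 1.960 = 0.947, and Φ(0.947) = 0.828, which reproduces 83%. (The noncentral t with 18 df gives 78.5%.) The figure concerns mean F. nucleatum. The documents give no effect size or variance for a community comparison, so every community figure below rests on assumed inputs.

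**2. What each planned analysis delivers on arm.**

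| Analysis | Uses arm | Error-controlled | Tests overall composition |
|---|---|---|---|
| F. nucleatum, t-test | yes | yes | no, one species |
| Gram-negative share, Wilcoxon | yes | yes | no, one sum per sample |
| Phyla and taxa, Benjamini-Hochberg | yes | yes | no, one taxon at a time |
| Shannon index | only via the general tests | only via the general tests | no, within-sample diversity |
| UniFrac and count-based distances | no test attached | no | would, if tested |
| Ordination and clustering | no | no | descriptive only |

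The general t, Wilcoxon and Fisher tests are univariate and do not apply to a distance matrix.

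**3. Can the adjusted taxon tests stand in?** Partly. If no taxon differs, every rejection is false, so the false discovery rate equals the probability of any rejection. Benjamini-Hochberg at 0.05 (level assumed from the general significance rule) holds this at or below 5% for independent or positively dependent tests. At least one significant taxon is then valid evidence that the arms differ. What remains is power, and the lack of a single measure of effect.

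**4. Power, 10 per arm.** Assumed: 60 taxa, between-subject SD 1.0 on the natural-log scale, 30% of taxa (18) lowered, Bray-Curtis distance; where needed, taxon means with SD 1.5 and 5,000 reads per sample. Ranges are over repeated runs. With 400 simulated trials, the standard error near 70% is √(0.7 × 0.3/400) = 0.023.

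| Shift (fold) | PERMANOVA | Any adjusted taxon, Wilcoxon | Any adjusted taxon, t on logs |
|---|---|---|---|
| none | 4.8–5.8% | 1.3% | 4.5% |
| 1.0 (e^1.0 = 2.7) | 36–41% | 16% | 41–44% |
| 1.5 (e^1.5 = 4.5) | 70.5–79% | 66–69% | 90–92% |
| 2.0 (e^2.0 = 7.4) | 85–90% | 96–97% | 99.5–100% |

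For diffuse small shifts the order reverses: PERMANOVA 49%, against 12% (Wilcoxon) or 34% (t on logs). The same ordering appears when every taxon moves a little, half up and half down. The plan does not say which test it will use for single taxa.

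**5. Level of the distance.** Assumed: 5 phyla of 20 OTUs, 5,000 reads, Dirichlet concentration 10, 20 or 40, and 30% of abundance moved within phyla so that phylum totals do not change. OTU-level PERMANOVA rejects in 49%, 86% and 99% of runs. Phylum-level distances reject in 4–6%, the chance rate, as the construction implies. This matters only if the phylum option is chosen.

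**6. Feasibility.** Unrestricted, 10 against 10 allows C(20,10) = 184,756 allocations. Randomization is stratified by reflux and regular PPI use, which makes four strata if both are yes/no. With five subjects in each, split 2 and 3, C(5,2)^4 = 10^4 = 10,000 allocations remain, which is ample. A stratum with one subject, or with all subjects in one arm, adds none.

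**The case against.** The strongest reply is that the trial's formal questions are its two F. nucleatum hypotheses, which are properly tested, and that ordination and clustering only supplement other tests. That is largely right. A reader might infer that the plan has no error-controlled answer on the microbiome and relies on looking at plots. The documents do not support this: cardia and esophageal F. nucleatum, the Gram-negative share, and phyla and taxa all have formal comparisons. For strong shifts in a minority of taxa, the adjusted taxon tests do about as well as PERMANOVA or better.

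Three further inferences are tempting and also fail.

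- **Clustering has a known, poor detection rate.** Any such rate needs a linkage, a number of clusters and a rule relating clusters to arm. The plan states none, so a ratio of clustering to PERMANOVA would measure an invented procedure.
- **Several specimens per subject inflate false positives.** The plan nowhere pools specimens as independent in a test. It handles saliva, swab, cardia and esophagus separately, with within-subject change for the oral samples.
- **Phylum-level work hides F. nucleatum.** That species is measured directly by qPCR, and phylum level is only one of the options listed.

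What stands after this is narrow: overall composition has no test or effect size, and the marginal tests can have less power when many taxa each move a little.

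**Conclusion.** The point holds in limited form. The plan computes between-sample distances and gives no inferential method for comparing them by arm. This follows from the text and depends on no simulation.

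The loss depends on the pattern of change. It is small or nil for strong shifts in some taxa. For a diffuse small shift, under the assumed inputs, it is 49% power against 12% or 34%. These sizes are illustrative, because the documents supply no community variance or effect. In every pattern the plan also lacks a single measure of how much of the variation arm explains.

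The gap lies in a secondary analysis of a pilot. The primary F. nucleatum tests and the sample size are untouched.

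**What to change.** In the paragraph on additional 16S analyses:

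- Name one OTU-level distance, for example weighted UniFrac.
- For cardia and esophagus separately, with one sample per subject, test arm by PERMANOVA. Permute arm labels within the reflux-by-PPI strata where stratum sizes allow, and state the fallback where they do not. Report R-squared, the p-value and a check for unequal dispersion, since PERMANOVA can also respond to a difference in spread.
- For saliva and swab, test whether the Day 0 to Day 14 shift differs by arm. Use the subject as the permutation unit, so that a subject's two samples move together.
- Keep ordination and clustering as descriptive figures, and label the new tests exploratory.

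The cost is a few sentences and a standard routine run on distances already planned. The downside is one more exploratory test per site, four in all. No new samples, visits or subjects are needed.

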### **Specimen collections:**

At the Day 0 visit we will collect saliva and also swab the inside of the mouth (cheek, tongue, hard palate, and gingiva).

This will be repeated at the Day 14 visit prior to the upper endoscopy.

During the endoscopy, the following samples will be taken for study purposes: 2 brushings (1 from normal appearing esophagus (3 cm above the gastroesophageal junction) and 1 from the gastric cardia); and 2 biopsies (one each from the esophagus and gastric cardia).

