### **Microbiome and tissue analyses:**

*F. nucleatum*. We will quantitatively assess absolute abundance of *F. nucleatum* from specimens via qPCR of the FadA adhesin gene.

16S rRNA gene sequencing. At the end of the study, we will perform batched DNA extraction performed using the Qiagen DNeasy Blood and Tissue Kit (Qiagen, Valencia, CA). We will perform PCR targeting the V3 and V4 hypervariable variable regions of the 16S rRNA gene with 347f/803r primers derived from the human microbiome project. We will pool and purify samples with the QIAquick PCR kit and perform library quantification using a KAPA Library Quantification Kit (Kapa Biosystems, Wilmington, MA).

Sequencing of the 16S rRNA gene V3 and V4 regions will be performed at the New York Genome Center using the Illumina MiSeq 300PE platform (Illumina, San Diego, CA).

Based on taxonomic assignments from the 16S sequencing analyses, we will calculate relative abundance of genera and species identified in the samples. We will subsequently assign each of these taxa as Gram-negative or not Gram-negative, based on our previously assembled reference list. We will then sum the relative abundances of each of the Gram-negative taxa to calculate the relative abundance of Gram-negative bacteria for each sample.

Inflammatory Cytokines, Stem Cell Proliferation, and Intestinalization. We will perform qRT-PCR on tissue biopsies to assess for levels of NF-B, IL-1, IL-6, and IL-8. In order to assess whether Gram-negative bacteria induced inflammation may lead to BE, we will also perform qRT-PCR and IHC (with available antibodies) of markers of intestinal progenitor cell activation (Lgr5, Notch, Cck2r, Dclk1, Bmp4) and intestinalization (Cdx2, Sox2, Tff2, Tff3).

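### Do the tissue-marker comparisons need a multiplicity adjustment because the taxa analyses have one?

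*Combined protocol and SAP*

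**What the plan says.** The section on microbiome and tissue analyses lists the markers. It begins "We will perform qRT-PCR on tissue biopsies to assess for levels of" four inflammatory markers, then adds five markers of progenitor-cell activation and four of intestinalization. These last nine are also to be examined by IHC where antibodies are available. Specimen collections provides for "2 biopsies (one each from the esophagus and gastric cardia".

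In Statistics, the markers appear under other secondary analyses, where the arms are compared on "levels of the above prespecified inflammatory cytokines and markers of stem cell proliferation and intestinalization". The tests are given in general terms: "We will use t-tests and Wilcoxon rank sum tests to compare continuous data". The threshold follows: "All analyses will be 2-sided, and statistical significance will again be defined as" p < 0.05.

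The preceding paragraph, on additional 16S analyses, treats phyla and individual taxa differently and names the Benjamini-Hochberg "method to adjust for multiple hypothesis testing". For the relative abundance of Gram-negative bacteria the section is specific about the test: "For these analyses we will use Wilcoxon rank sum tests instead of t-tests". It introduces the whole group of analyses with "We will perform numerous additional secondary analyses as part of this pilot study".

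**The concern.** Two features draw attention. First, the plan adjusts for multiplicity in one paragraph and says nothing about it in the next, although 13 or more marker comparisons are enough for chance findings to be likely. Second, the adjusted analyses of individual taxa are the ones labelled exploratory, while the unadjusted markers are called prespecified and can be declared significant.

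Sample Size Considerations says that, if the mouthwash shows no significant effect on *F. nucleatum*, the secondary analyses should still help in designing later studies. A marker that crossed 0.05 by chance could therefore steer follow-up work. The plan also leaves open whether both biopsy sites are compared and which of the two named tests applies to the markers. Read together, this could look like an uncontrolled family of tests with a loosely defined analysis.

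**Working it through.** **Inputs.** Marker counts come from Microbiome and tissue analyses, the two sites from Specimen collections, the threshold from Statistics, and 10 per arm and 1.3 SD from Sample Size Considerations. The documents give no effect size or correlation for the markers. The 1.3 SD is the plan's figure for *F. nucleatum* and is borrowed here as an assumption; correlations of 0, 0.5 and 0.8 are also assumed.

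**1. The plan's own power figure.** By the two-sided normal approximation, power = Φ(1.3/√(2/10) − 1.96) = Φ(2.907 − 1.960) = Φ(0.947) = 0.828. This matches the stated 83%. The exact two-sided t-test gives 0.785, so about 78% is the realistic unadjusted power for any one marker that shifts by 1.3 SD.

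**2. Number of comparisons.** By qRT-PCR: 4 + 5 + 4 = 13 at one site and 13 × 2 = 26 at two. If IHC were possible for all nine eligible markers at both sites, 9 × 2 = 18 would be added, giving 44. The count therefore lies between 13 and 44, and 26 is not a ceiling.

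**3. What chance alone produces.** The expected number below 0.05 is 0.05m. The probability of at least one, with independent tests, is 1 − 0.95^m. The last column is simulated.

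| Tests (m) | Expected by chance | At least one, independent | At least one, correlation 0.5 |
|---|---|---|---|
| 13 | 0.65 | 0.487 | 0.34 |
| 26 | 1.3 | 0.736 | 0.49 |
| 44 | 2.2 | 0.895 | 0.62 |

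At correlation 0.8 the chance falls to about 20% for 13 tests and 26% for 26.

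**4. How many calls would be false.** Suppose one of 13 markers truly moves by 1.3 SD. Expected false calls are 12 × 0.05 = 0.60 and expected true calls 0.78, so the pooled share of false calls is 0.60/(0.60 + 0.78) = 0.43. Expected counts do not depend on correlation, so this share is the same at every correlation. A different measure averages the false share per trial and scores trials without any call as zero; it gives 0.30, 0.23 and 0.15 at correlations 0, 0.5 and 0.8. If four of 13 move, the pooled share is 9 × 0.05/(9 × 0.05 + 4 × 0.78) = 0.45/3.57 = 0.13.

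**5. Does the plan break a rate it states?** It states a two-sided 0.05 threshold for each comparison. In null simulations at 10 per arm, the t-test rejects in 5.0% and the exact Wilcoxon test in 4.3%. Counting a marker if either test is significant gives about 5.7% with normal data. The stated rate is essentially met, and leaving the test open moves it very little.

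**6. What adjustment would do.** With BH as the decision rule for 13 tests, power for a lone 1.3 SD marker falls from about 0.78 to about 0.38. With four true markers it is about 0.52 each. For 26 tests and one true marker it is about 0.29. With BH values only displayed beside the raw p-values, every estimate, interval and raw p-value stays as it was.

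**The case for a change.** The strongest contrary case is that the remedy is nearly free. BH is already in the plan, one more table column would show it, and unadjusted values would stay beside it, so the usual complaint about lost power in a small pilot does not arise. Meanwhile, in the one-true-marker scenario, about four in ten markers called significant would be false, and the plan intends these results to inform later work.

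The arithmetic stands, and such a column would do no harm. It is also true that the sites and the single test for the markers are not stated. That is missing detail, and for the choice of test the effect is shown above to be small.

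The argument does not establish a fault. A display that decides nothing alters no result; its only effect would be on the word used to describe a p-value below 0.05. A BH rule that did decide would be a real trade-off, roughly halving power when few markers respond, and competent statisticians differ on whether a pilot should accept that. A BH family confined to the qRT-PCR markers within each site would also leave any IHC comparisons outside it and would not adjust across sites.

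Nor is the contrast with taxa an inconsistency. The number of taxa is unknown until sequencing is done, and testing them is a screen. The markers are a short list named in advance with a stated biological rationale. A reader has both the list and the threshold, and can work out 13 × 0.05.

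**Conclusion.** The concern does not hold. Unadjusted two-sided 0.05 tests on named secondary outcomes are an accepted choice in a pilot of 10 per arm. The plan claims no error control across the markers, so none is violated. The two main hypotheses, on *F. nucleatum* in saliva and in the gastric cardia, do not depend on these comparisons.

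Chance findings among the markers are likely: 0.65 expected in 13 tests and 1.3 in 26 if nothing moves. Readers should keep that in mind, but it follows openly from what the plan states. The family-wide probabilities depend on the assumed correlations. The false-call shares and power figures depend on the assumed 1.3 SD effect and the number of markers that truly respond. The conclusion does not rest on any of these assumptions, because it turns on what the plan promises and what the marker results are for.
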